1.0 LIST OF ABBREVIATIONS

| Abbreviation | Term |
|--------------|---|
| IOP | Intraocular pressure |
| ICH | International Conference on Harmonisation |
| IRB | Internal review board |
| ITT | Intention to treat |
| GCP | Good Clinical Practice |
| LH | [name] |
| LOCF | Last Observation Carried Forward |
| mm Hg | Millimeters Mercury |
| POD | Post-operative day |
| POW | Post-operative week |
| POM | Post-operative month |

2.0 STUDY FLOW CHART

| | | | Study Day | | | | | |
|---|----------------------------|-----------------------|-------------------------|-------------------------|-------------------------|--------------------------|---------------------------|--------------------------|
| | | | | | | | | |
| | Screening / Baseline visit | Post-Op Day 1 ± 1 day | Post-Op Week 1 ± 5 days | Post-Op Week 4 ± 1 week | Post-Op Week 6 ± 1 week | Post-Op Month 3 ± 1 week | Post-Op Month 6 ± 2 weeks | Post-Op Year 1 ± 1 month |
| Informed Consent | X | | | | | | | |
| Review inclusion and exclusion criteria | X | | | | | | | |
| Visual acuity assessment | X | X | X | X | X | X | X | X |
| Slit-lamp biomicroscopy | X | X | X | X | X | X | X | X |
| Applanation Tonometry | X | X | X | X | X | X | X | X |
| Subjective diplopia | | X | X | X | X | X | X | X |
| Pachymetry | X | | | | | | | X |
| Direct fundus exam | X | | | | | | | X |
| Humphrey visual field | X | | | | | | | X |
| Optical coherence tomography | X | | | | | | | X |
| Self-report dysesthesia scale | X | | | | | | | X |
| Motility history and exam | X | | | | | | | X |
| Quality of life questionnaires | | | | | | | | X |

X procedure performed at the time of clinic visit

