The Ahmed ClearPath is a newly developed non-valved glaucoma drainage device that entered United States markets in late 2019 (New World Medical, Inc., Rancho Cucamonga, CA) (Figure 2). This device comes in two sizes: a 250 mm^2 model (Figure 3A) and a 350 mm^2 model (Figure 3B). We will be focusing on the 350 mm^2 model which will be the only variant of the ClearPath evaluated in this study. There are several features of the ClearPath that are advertised as advantageous compared to the Baerveldt. For instance, the 350 mm^2 model features a posteriorly positioned plate in order to avoid intraocular muscle attachment points upon insertion. It has a flexible, contoured design and anteriorly positioned suture points which are intended to optimize the process of device implantation for the surgeon, though this has not yet been confirmed. As it is non-valved implant, it also requires early restriction for the same reasons mentioned for the Baerveldt. However, the ClearPath device comes packaged with a pre-threaded 4-0 polypropylene ripcord though some surgeons do replace this with sutures of differing materials or size per preference.

[figure not shown]

Figure 3. The Ahmed ClearPath 250 mm^2 (A) and 350 mm^2 (B) (www.newworldmedical.com).

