7.3 Post-operative visit year 1 (± 1 month)

The subject will undergo a standard of care post-operative assessment of visual acuity, slit lamp biomicroscopy, and tonometry. At the year 1 post-operative visit, subjects will also undergo visual field testing, optical coherence tomography, pachymetry, and motility testing. Subjects will also complete self-report questionnaires pertaining to dysesthesia and quality of life.

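### The post-op diplopia question has no matching baseline item, so new-onset and pre-existing diplopia cannot be reliably separated; quality of life also has no baseline

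*Combined protocol and SAP*

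**What the plan says.** The relevant rows of the Section 2.0 flow chart have eight visit columns: Screening/Baseline, then seven post-op visits.

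- Diplopia, listed as "Subjective diplopia": the row reads "Subjective diplopia | | X | X | X | X | X | X | X". The baseline cell is blank and every post-op cell is marked.
- Quality of life: "Quality of life questionnaires | | | | | | | | X". Only Year 1 is marked.
- Motility: "Motility history and exam | X | | | | | | | X". Baseline and Year 1.
- Dysesthesia: "Self-report dysesthesia scale | X | | | | | | | X". Baseline and Year 1.

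The text agrees with the chart. Section 5.5 lists the baseline data, including ocular history, a motility exam and the dysesthesia scale, but no diplopia question and no quality-of-life instrument. Section 7.3 places quality of life at Year 1: "Subjects will also complete self-report questionnaires pertaining to dysesthesia and quality of life".

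Complication rates are part of the objective (Section 4.0) and of the null hypothesis (Section 8.1.2). Section 8.1.4 plans Student t tests and chi-square or Fisher tests and names no baseline adjustment. No section lists the complications, gives a rule for counting diplopia, or says how diplopia present before surgery is handled.

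**The concern.** Every other assessment in the flow chart is marked at baseline; these two are the exceptions. The gap matters more for diplopia. Section 3.1 reports as an advertised feature that the 350 mm² ClearPath "features a posteriorly positioned plate in order to avoid intraocular muscle attachment points upon insertion". Diplopia is thus a complication on which the two devices could plausibly differ.

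A background of zero cannot be assumed. Section 6.2 does not exclude pre-existing diplopia, and Section 6.1 admits traumatic glaucoma and eyes with earlier intraocular surgery. If subjects who already saw double are mixed with new cases, both arms' rates rise and the contrast shrinks. Since Section 3.2 hypothesises no difference in complication rates, a diluted comparison makes a null finding less informative.

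For quality of life less is at stake: change from baseline and comparability of the arms at baseline cannot be described, and the Year 1 score cannot be adjusted for its own starting value.

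**Working it through.** **The plan's own figure.** Inputs from Sections 5.3 and 8.1.3: difference 2 mmHg, SD 5.9 mmHg, two-sided alpha 0.05, power 80%, dropout 10%.

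n per arm = 2 × (1.96 + 0.842)² × 5.9² / 2² = 136.6, so 137. Then 137 / 0.9 = 152.2, which agrees with the stated 152. This figure concerns IOP and is not affected by the present point. It supplies the 137 evaluable subjects per arm used below.

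**Diplopia.** The documents give no rates, so all rates here are assumptions. Let b be the share of subjects with persistent pre-existing diplopia, equal in both arms, and p the new-onset rate (5% in one arm, 15% in the other).

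- Observed rate if background cases are counted: q = b + (1 − b)p.
- Power = Φ[(d − 1.96 × SE₀) / SE₁], where d is the difference in rates, SE₀ = √(2q̄(1 − q̄)/n) uses the mean rate q̄, and SE₁ = √([q₁(1 − q₁) + q₂(1 − q₂)]/n).

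Example with b = 5%: q₁ = 0.05 + 0.95 × 0.05 = 0.0975; q₂ = 0.05 + 0.95 × 0.15 = 0.1925; d = 0.095; SE₀ = 0.0425; SE₁ = 0.0422. Power = Φ[(0.095 − 0.0834)/0.0422] = Φ(0.28) = 61%.

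The background cases can be separated in two ways: exclude them, leaving n = 137(1 − b) at 5% vs 15%; or keep them in the denominator as non-events, giving rates (1 − b)p with n = 137.

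| b | Observed rates | Difference (points) | Power, counted | Power, excluded | Power, kept as non-events |
|---|---|---|---|---|---|
| 0% | 5.0 vs 15.0% | 10.0 | 79% | 79% | 79% |
| 2% | 6.9 vs 16.7% | 9.8 | 71% | 78% | 78% |
| 5% | 9.8 vs 19.3% | 9.5 | 61% | 77% | 77% |
| 10% | 14.5 vs 23.5% | 9.0 | 48% | 75% | 74% |

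Most of the loss comes from the larger variance at higher rates, not from the small shrinkage in the difference. With a smaller assumed contrast of 5% vs 10%, power is only 35% to begin with. It falls to 28%, 22% or 17% when background cases are counted, against 34%, 33% or 32% when they are excluded.

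**Quality of life and dysesthesia.** With r the correlation between baseline and Year 1 scores (not given in the documents), ANCOVA multiplies the variance by 1 − r². The difference detectable with 80% power, in SD units, is (1.96 + 0.842) × √(2(1 − r²)/137).

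| r (assumed) | Variance reduction | SE reduction | Detectable difference |
|---|---|---|---|
| 0 | 0% | 0% | 0.338 SD |
| 0.3 | 9% | 5% | 0.323 SD |
| 0.5 | 25% | 13% | 0.293 SD |
| 0.7 | 49% | 29% | 0.242 SD |

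A simple change score has variance 2(1 − r) times that of the Year 1 score, so it gains precision only when r exceeds 0.5.

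**The case against.** The strongest reply is that the baseline motility history is a natural place to record earlier double vision, and Section 5.5 adds ocular history and a motility exam. If that history does record diplopia, known cases can be separated with no new data and most of the power loss disappears. This stands in part. It may capture some cases, but its content is unspecified, Section 5.5 names only the exam, and nothing links it to the question repeated after surgery.

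Three stronger readings are tempting and are not supported.

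- A reader might infer that the plan counts pre-existing diplopia as a post-op complication. No section says so; there is no counting rule either way.
- A reader might infer bias between the devices. Subjects are randomised (Section 5.6), so background diplopia is balanced in expectation. The harm is inflated rates and dilution.
- A reader might infer that the quality-of-life comparison fails without a baseline. A Year 1 comparison of randomised arms is valid. Quality of life is in neither the hypothesis nor the sample size, and a baseline score would add no precision under an unadjusted t test.

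It is also fair to say that the size is entirely assumed. The 5% vs 15% contrast is a tripling, the model lets every baseline case persist and be counted, and Section 8.0 promises only descriptive statistics for safety assessments. If diplopia is only described, the cost is inflated rates that are harder to interpret rather than a weaker test. These points limit the figures to illustration but do not remove the gap.

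**Conclusion.** The point holds as a minor design gap. Neither the chart nor the text provides a like-for-like baseline for the diplopia question, and no rule separates new from pre-existing cases.

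Under the assumed 5% vs 15%, with 137 per arm and 2% to 10% background, counting background cases would lower power from 79% to between 71% and 48%. Separating them, by either method, keeps it between 78% and 74%. These results depend on rates the documents do not give, and the loss is smaller to the extent that the motility history records earlier diplopia.

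For quality of life, the possible gain is a 9% to 49% reduction in variance at an assumed correlation of 0.3 to 0.7, and only with a baseline-adjusted analysis. The same range applies to dysesthesia, whose baseline is already collected but has no stated role in the analysis. None of these outcomes drives the sample size.

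**What to change.** 1. Mark the subjective diplopia question at Screening/Baseline in Section 2.0 and add it to the Section 5.5 list, worded as it is after surgery.
2. In Section 8.1.4, define the diplopia outcome as new onset among subjects without diplopia at baseline. Add worsening only if the item is graded; a yes/no answer cannot show it.
3. Analyse Year 1 dysesthesia by ANCOVA on the baseline score in place of the unadjusted t test. This needs no new data.
4. Optionally, give the quality-of-life questionnaires at baseline too, and use ANCOVA for the Year 1 score. Adding the baseline without changing the analysis would gain no precision.

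The cost is one extra question at a visit where a self-report scale is already completed, plus, if step 4 is taken, questionnaires whose number and length the documents do not state. Subjects already operated on would lack the new baseline values. For them the motility history should be reviewed for earlier diplopia, and the analysis should state how they are handled.

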3.0 INTRODUCTION

3.1 Background

Implanting aqueous drainage devices has become an increasingly common surgical treatment for glaucoma. Medicare data between 1995 and 2004 demonstrated a steady increase in the use of these devices.^{1,2} Even with the advent of minimally invasive glaucoma surgery (MIGS), aqueous drainage devices is still a mainstay of treatment for uncontrolled intraocular pressure (IOP).³ Currently, one of the most common aqueous drainage devices used is the Baerveldt implant (Johnson & Johnson, Vision, Jacksonville, Florida) (Figures 1&2).

[figure not shown]

Figure 1. Schematic of the different Baerveldt Implant Models available. On the far most right is the Baerveldt 101-350 model that will be utilized in this study.

[figure not shown]

Figure 2. Depiction of typical Baerveldt implant once positioned and implanted on the eye.
www.towerclockeyecenter.com

The Baerveldt implant is an FDA-approved silicone, non-valved implant. This device comes in 3 variants: a single 250 mm² model and two 350 mm² models (Figures 1&2). For the purposes of this study, we will be focusing on the Model BG-101-350, (Figures 1&2) which will be the only variant of the Baerveldt evaluated in this study. As it is non-valved, it needs early restriction of fluid flow to minimize hypotony while the eye forms a fibrous capsule around the implant. One common way of restricting fluid flow is by ligating or tying off the Baerveldt tube with an absorbable suture that dissolves by post-operative week 4 to 6. For better control of the tube opening and intraocular pressure reduction during the post-operative

period, many surgeons place a suture within the lumen of the implant, called a ripcord, at the time of surgery. This ripcord suture is accessible at the slit lamp in clinic.

The Ahmed ClearPath is a newly developed non-valved glaucoma drainage device that entered United States markets in late 2019 (New World Medical, Inc., Rancho Cucamonga, CA) (Figure 2). This device comes in two sizes: a 250 mm^2 model (Figure 3A) and a 350 mm^2 model (Figure 3B). We will be focusing on the 350 mm^2 model which will be the only variant of the ClearPath evaluated in this study. There are several features of the ClearPath that are advertised as advantageous compared to the Baerveldt. For instance, the 350 mm^2 model features a posteriorly positioned plate in order to avoid intraocular muscle attachment points upon insertion. It has a flexible, contoured design and anteriorly positioned suture points which are intended to optimize the process of device implantation for the surgeon, though this has not yet been confirmed. As it is non-valved implant, it also requires early restriction for the same reasons mentioned for the Baerveldt. However, the ClearPath device comes packaged with a pre-threaded 4-0 polypropylene ripcord though some surgeons do replace this with sutures of differing materials or size per preference.

[figure not shown]

Figure 3. The Ahmed ClearPath 250 mm^2 (A) and 350 mm^2 (B) (www.newworldmedical.com).

3.2 Rationale

Previous studies have compared the efficacy of the Baerveldt to the older, valved Ahmed FP7 glaucoma drainage device (Ahmed Glaucoma Valve; New World Medical, Inc., Rancho Cucamonga, CA). These studies have yielded mixed results, and many surgeons will opt to use either a Baerveldt or an Ahmed FP7 depending on a number of patient-dependent factors. However, there is currently no data published comparing the Baerveldt to the new, non-valved Ahmed ClearPath. We are interested in performing a head-to-head trial in order to compare overall efficacy and failure rates of the Baerveldt as compared to the ClearPath. Criteria for device failure includes: IOP $> 18 \text{ mmHg}$ or not reduced by 20% less than baseline on two consecutive visits after three months, IOP $< 6 \text{ mmHg}$ on two consecutive visits after three months, need for additional glaucoma surgery or device removal, and the loss of light perception vision. Given the similarities in design, in particular the equal sizes of the implant plate, we hypothesize that there is no difference in the efficacy of IOP reduction or complication rates in patients who undergo Baerveldt implant versus those who undergo ClearPath implants. However, this cannot be verified without sufficient investigation. The results of this study will provide important data for surgeons to select the most appropriate device to achieve favorable outcomes while minimizing complications.

4.0 OBJECTIVE

To compare the post-operative surgical outcomes and complication rates in patients with a Baerveldt 350 aqueous drainage device (model 101-350; Johnson & Johnson, Vision) vs the Ahmed ClearPath implant (350 mm²; New World Medical, Inc., Rancho Cucamonga, CA).

5.0 STUDY DESIGN AND METHODS

5.1 Experimental Design

This is a randomized prospective study of post-operative surgical outcomes and complication rates in patients with a Baerveldt 350 implant vs the Ahmed ClearPath implant. Each subject will be randomized to the Baerveldt group or ClearPath group at the time of consent for the study. A baseline eye exam will be conducted as per the study flowchart (Section 2). Surgeons will include

- [name]
- [name]
- [name]
- [name]
- [name] [name]
- [name]
- [name], PhD
- [name], PhD
- [name]
- [name]
- [name]
- [name], PhD
- [name]
- [name]

It will not be possible for the surgeon to be masked given that s/he will be implanting the device. The subject will then be seen on post-operative day 1 (± 1 day), week 1 (± 5 days), week 4 (± 1 week), week 6 (± 1 week), month 3 (± 1 week), month 6 (± 2 weeks) and year 1 (± 1 month) as per the standard-of-care post-operative schedule. At each of these post operative visits, ophthalmic exams will be conducted, collecting data such to be in accordance with the study flowchart (Section 2).

5.2 Subject Selection

Subjects will be identified from patients presenting for ophthalmologic consultation at the Duke Eye Center and/or one of its satellite clinical locations. Individuals with uncontrolled glaucoma are routinely available from this clinic and will be the primary study group. A care provider known to the patient will introduce the study and his/her ophthalmologist will be asked for prior approval to enroll the patient. The target enrollment will be approximately 304 subjects. Subjects will not be compensated for participation. All adults meeting study criteria (as detailed in Section 6.0) will be asked to participate.

Informed consent will be obtained for each patient. The surgeon or his/her study staff will initially approach potential subjects for consent. During the consent process, the person obtaining consent will inform the potential subject of all elements of informed consent and shall discuss the nature of the study, its requirements and its restrictions. Adequate time will be allowed for the potential subject to ask questions prior to deciding whether to participate in the study.

5.3 Sample Size

Approximately 152 subjects will be enrolled in each treatment group for a total of approximately 304 subjects. This sample size was based on a power analysis aimed at detecting a 2 mmHg difference in IOP between the Baerveldt and ClearPath groups with 80% power, using the mean post-op year 1 Baerveldt IOP of 13.6 ± 5.9 mmHg from the pooled AVB and ABC data.⁴ The results were adjusted for an expected 10% drop out rate at 1 year.

5.4 Baseline Evaluation

The initial evaluation for glaucoma and need for surgical intervention will include a standard-of-care ophthalmic examination that is performed by a licensed ophthalmologist. Collection of all data will be under the supervision of a licensed ophthalmologist

5.5 Study Evaluation

If the potential subject meets the criteria for study-inclusion and consents to participate following full explanation of the research, the subject will be randomly assigned to either group. The subject's baseline exam findings will be documented, including: age, sex, race, glaucoma diagnosis and cause, ocular history (including prior treatments and procedures), best-corrected Snellen visual acuity, IOP by Goldmann applanation tonometry (masked, 2-person), glaucoma medications, slit lamp findings, external exam findings, motility exam, Humphrey Visual Field, Optical Coherence Tomography, and a patient reported-reported dysesthesia scale.

5.6 Randomization and Masking

At the time of consent, subjects will be randomized to receive either the Baerveldt or ClearPath according to a computer-generated randomization code. Study subjects will be masked as to which implant they will receive. In the patient chart, the device will be noted at a glaucoma drainage device (GDD).

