8.1 Statistical Considerations

8.1.1 Analysis Plan

The Intent-To-Treat (ITT) population includes all randomized subjects who had at least one post-op assessment. The primary efficacy analysis will be performed on the ITT population with Last Observation Carried Forward (LOCF). If a subject is deemed to have a failed surgery and undergoes a rescue procedure, the last observation collected prior to the intervention will be used for efficacy analyses at all later timepoints.

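### Randomization at consent, combined with a primary set that omits randomized subjects who have no post-operative assessment, leaves room for pre-surgery losses to differ by arm

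*Combined protocol and SAP*

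**What the plan says.** All places are in the combined protocol and SAP.

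- **Timing of assignment.** Section 5.1: "Each subject will be randomized to the Baerveldt group or ClearPath group at the time of consent for the study". Section 5.6 repeats this: "At the time of consent, subjects will be randomized to receive either the Baerveldt or ClearPath".
- **Order relative to baseline.** In Section 5.1 the sentence after the one on randomization reads "A baseline eye exam will be conducted as per the study flowchart (Section 2)". Section 5.5 says that if a person meets the criteria and "consents to participate following full explanation of the research, the subject will be randomly assigned to either group"; the next sentence lists the baseline findings to be documented. The flow chart in Section 2.0 puts consent and the baseline tests in a single screening/baseline column.
- **Masking.** Section 5.1 says the surgeon cannot be masked, because he or she implants the device. Section 5.6 masks subjects and has the chart record only a generic drainage device. Section 5.5 lists baseline "IOP by Goldmann applanation tonometry (masked, 2-person)".
- **Analysis set.** Under Section 8.1.1 the ITT population "includes all randomized subjects who had at least one post-op assessment", and the primary efficacy analysis uses that set with LOCF.
- **Not stated.** The documents do not say who sees the assignment or when it is released, how long the interval from consent to surgery is, or how randomized subjects left out of the primary set will be reported.

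**The concern.** Randomization protects the comparison only if what happens between assignment and entry to the analysis does not depend on the arm. Here surgery falls in that interval, and a subject enters the analysis only after a post-operative visit. The first scheduled visit is on day 1, so nearly everyone operated on will qualify. Those left out are chiefly people who were randomized and then not operated on.

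Several decisions are still open in that interval, and the surgeon can influence them:

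- the quadrant and surgical technique (Section 7.1);
- whether another procedure is added, which Section 6.2 lists as an exclusion;
- withdrawal at the investigator's request (Section 9.5).

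If the surgeon or the consenting staff know the device during that time, any of these could differ by arm. The analysis could not detect or undo the effect, because the affected subjects are not in it. The ITT label would also tell readers that everyone randomized had been counted.

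**Working it through.** **1. The plan's own sample size.** Inputs: difference 2 mmHg, SD 5.9, 80% power and 10% dropout (Section 5.3); two-sided alpha 0.05 (Section 8.1.3).

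n per arm = 2 × [5.9 × (1.960 + 0.842) / 2]² = 136.6

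136.6 / 0.90 = 151.8, which agrees with the stated 152. The sample size is not in dispute.

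**2. Bias from one-arm exclusion.** Let f be the excess share of one arm that is randomized but excluded. Let D be the amount by which their year-1 IOP would have exceeded that of the retained subjects, had they been operated on and followed. If the retained mean is m, the mean for the whole arm is (1 − f)m + f(m + D) = m + fD. Analysing only the retained subjects therefore shifts the arm difference by

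bias = f × D

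The documents give neither f nor D, so both are assumptions.

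| f (one arm) | D (mmHg) | Bias (mmHg) | Share of 2 mmHg |
|---|---|---|---|
| 2% | 5 | 0.10 | 5% |
| 2% | 10 | 0.20 | 10% |
| 5% | 5 | 0.25 | 12.5% |
| 5% | 10 | 0.50 | 25% |

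For scale, 2% and 5% of 152 are about 3 and 8 subjects, and 5 to 10 mmHg is 5/5.9 = 0.85 to 10/5.9 = 1.7 SD.

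**3. Effect on the test.** Under no true difference, with 152 in one arm and 152(1 − f) in the other, SE = 5.9 × √[1/152 + 1/(152(1 − f))].

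- f = 2%, D = 5: SE = 0.680, bias/SE = 0.15, two-sided type I error about 0.052.
- f = 5%, D = 5.9 (one SD): bias = 0.30, SE = 0.686, bias/SE = 0.43, type I error about 0.072.
- f = 5%, D = 10: bias/SE = 0.73, type I error about 0.113.

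**4. Power.** LOCF keeps later dropouts in the primary set, so pre-surgery loss has to be taken from 152. A 5% loss in both arms leaves 144.4 per arm and power of about 0.82. A 10% loss leaves 136.8 and about 0.80. Power is not the problem here.

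**The case against.** Four points on the other side have weight.

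- **Disclosure is not stated.** A reader might infer that the code is opened to surgeons at consent. The documents do not say so. Section 5.1 ties the surgeon's lack of masking to implanting the device. What can be said is that concealment between assignment and surgery is not described. This point stands.
- **Baseline readings have some protection.** A reader might infer that baseline IOP will be read with the device known. Section 5.5 describes a masked two-person reading. It does not say whether the masking is to arm or to the tonometer value. Consent and baseline share one visit column, so the exam may precede assignment in practice. Baseline IOP enters the 20%-reduction failure criterion in Section 3.2; the sample size is built on year-1 IOP. The baseline limb is therefore secondary.
- **Other safeguards exist.** Section 5.5 already puts eligibility ahead of assignment. Masked subjects are less likely to withdraw over device preference. Neither safeguard limits a surgeon who knows the arm.
- **The size is assumed.** The 0.5 mmHg figure is the extreme corner of the table, and milder cases are small. A reader might also infer a loss of power below target, but step 4 shows that the plan's LOCF rule does not support this for losses up to 10%.

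None of these answers the main point, which is that assignment comes before surgery and entry to the primary set depends in practice on surgery taking place.

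**Conclusion.** The concern holds as a structural weakness. The plan allocates earlier than it needs to, does not say who knows the allocation before surgery, and defines its primary set by an event after randomization that the surgeon can influence. Under the stated assumptions the bias is 0.1 to 0.5 mmHg, or 5% to 25% of the target difference. It is zero if losses are equal in the two arms and unrelated to outcome. The documents do not show that differential loss will occur. Since the plan calls for no by-arm account of unanalysed subjects, readers would have no assurance that it had not. The change should be made: it is inexpensive, and the order of steps cannot be repaired for subjects already randomized.

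**What to change.** **Sections 5.1, 5.5 and 5.6.** State that the baseline exam and the planned quadrant are completed and recorded before assignment. Generate or release the allocation as close to surgery as practical, ideally on the day of surgery. State who learns it and when, and say what masked means for the baseline IOP reading.

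**Section 8.1.1.** Do not call the set ITT without qualification; describe it as randomized subjects with a post-operative assessment, analysed by assigned arm. Renaming it as all randomized subjects who had surgery would not be enough, since that leaves out essentially the same people. Report by arm, with reasons, every randomized subject who was not operated on or had no post-operative visit. Add a sensitivity analysis of all randomized subjects. Those with no post-operative value need a pre-specified assumption, for example a range of IOP values that may differ by arm.

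**Cost.** A protocol amendment that reorders existing steps, and one added table and analysis. The practical downside is that both marketed devices must be on hand at surgery. Recording baseline before assignment adds no procedure.

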6.0 INCLUSION/EXCLUSION CRITERIA

6.1 Inclusion Criteria

- Men or women with age at screening ≥ 18 years and ≤ 90 years
- Inadequately controlled glaucoma
- Valve-less aqueous shunt as the planned surgical procedure
- Patients with primary glaucomas or pseudoexfoliation, pigmentary and traumatic glaucoma with a previous failed trabeculectomy or other intraocular surgery included.
- Primary tubes included
- Investigators to recruit consecutively all eligible patients from their clinics.
- Superotemporal or inferonasal placement of the tube
- Capable and willing to provide consent

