7.1 Surgical Procedure

The patient will undergo standard superotemporal or inferonasal placement of either a Baerveldt or ClearPath implant, which may include placement of a suture ripcord as per the surgeon's preference. The methods utilized to place the tube will vary based on surgeon preference to enhance the generalizability of the results.

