8.1.3 Sample Size Considerations

With a 2-sided significance level of 0.05, a sample size of 152 in each group would be required to detect a 2 mm difference in IOP with 80% power (accounting for a 10% drop out rate). The total planned enrollment for this pilot study is approximately 304 subjects

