8.1.4 Statistical Methods

Descriptive statistical analysis of patient characteristics across the 2 treatment groups will be performed. Snellen VA measurements will be converted to logMAR equivalents for the purpose of data analysis. Student t test for continuous variables, Fisher exact test, and the χ^2 test, or exact permutation χ^2 test for categorical variables will be utilized. All tests will be 2-sided in accordance with our hypothesis. A P-value of 0.05 will be considered statistically significant.

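### The analysis of IOP adjusts for neither surgeon nor prior surgery: the planned t test is valid, but a prespecified adjusted model would recover a modest amount of precision

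*Combined protocol and SAP*

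**What the plan says.** **Surgeons.** Section 5.1 lists 14 bullet entries under surgeons. Names are removed and one bullet carries two name marks, so the count is approximate.

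**Technique and care.** Section 7.1 states: "The methods utilized to place the tube will vary based on surgeon preference to enhance the generalizability of the results". It also leaves ripcord placement to the surgeon. Section 7.2 leaves added glaucoma medication, ripcord removal and further glaucoma surgery to the surgeon's discretion.

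**Case mix.** Section 6.1 admits eyes with a failed trabeculectomy or other intraocular surgery, and adds "Primary tubes included". Section 5.5 records prior treatments and procedures at baseline. It does not list the operating surgeon as a data item.

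**Randomization.** Section 5.6 allocates each subject at consent "according to a computer-generated randomization code". It mentions no strata, blocks or minimization.

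**Analysis.** Section 8.1.4 names "Student t test for continuous variables", and Fisher, chi-square or permutation tests for categorical ones. No term for surgeon, prior surgery or any other covariate appears. Patient characteristics are to be compared descriptively between groups.

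**The concern.** The plan deliberately admits two sources of outcome variation besides the device: who operates and how, and whether the eye has been operated on before. Neither is described as controlled at randomization, and neither enters the analysis. Variation between surgeons and between primary and previously operated eyes therefore stays in the error term, and any chance imbalance passes unadjusted into the estimated device difference.

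This matters for two reasons. The design sits at 80% power with nothing to spare. Section 3.2 also expects no difference between devices, so the usefulness of the result depends largely on how narrow the confidence interval is. If an imbalance appears and the analyst then adjusts for it, the choice will look driven by the data unless it was fixed beforehand.

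**Working it through.** **Inputs from the documents.** Section 8.1.3: "With a 2-sided significance level of 0.05". Section 5.3: a sample size aimed at "detecting a 2 mmHg difference in IOP between the Baerveldt and ClearPath groups with 80% power", based on "the mean post-op year 1 Baerveldt IOP of 13.6 ± 5.9 mmHg from the pooled AVB and ABC data", and "adjusted for an expected 10% drop out rate at 1 year"; 152 per group. I take 5.9 mmHg as the SD of year 1 IOP.

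**Inputs assumed, because the documents give none.** The share of IOP variance due to surgeon and prior surgery (0% to 20%); half of eyes previously operated; a prior-surgery effect of 0 or 2 mmHg.

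**1. Reproduce the plan's figure.**
n = 2 × [5.9 × (1.960 + 0.842) / 2]² = 136.6 per group. Dividing by 0.9 gives 151.8, so the stated 152 reproduces (153 if 137 is rounded up first).
Power with 152 × 0.9 = 136.8 evaluable per group: SE = 5.9 × √(2/136.8) = 0.71 mmHg, power 80.1% (79.8% from the t distribution).

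**2. Best-case gain from adjustment.** If the factors explain a share R² of the variance and all of it is removed at no cost, the SD becomes 5.9 × √(1 − R²).

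| R² (assumed) | SD | Power at 136.8 per group | 95% CI half-width | N per group for 80% power, with dropout |
|---|---|---|---|---|
| 0% | 5.90 | 80.1% | 1.40 mmHg | 153 |
| 5% | 5.75 | 82.0% | 1.36 | 145 |
| 10% | 5.60 | 84.0% | 1.33 | 137 |
| 20% | 5.28 | 88.0% | 1.25 | 123 |

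**3. Simulated gain.** The simulation had 274 evaluable patients, 14 surgeons of unequal volume, unstratified allocation and 4,000 runs per setting. The adjusted model used fixed surgeon terms plus prior surgery. Monte Carlo error is about √(0.8 × 0.2/4000) = 0.6 points per figure.

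| Surgeon share | Prior-surgery effect | Power, t test | Power, adjusted |
|---|---|---|---|
| 0% | 0 mmHg | 79.2% | 77.1% |
| 0% | 2 mmHg | 79.0% | 78.1% |
| 5% | 0 mmHg | 79.9% | 79.6% |
| 5% | 2 mmHg | 78.8% | 79.5% |
| 10% | 0 mmHg | 79.8% | 81.8% |
| 10% | 2 mmHg | 80.5% | 83.8% |

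A 2 mmHg effect in half the eyes has variance 2² × 0.25 = 1, or 1/34.81 = 2.9% of the total, so the last row corresponds to about 13% explained.

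With a random surgeon intercept in place of fixed terms (1,500 runs), power was 80.9% for the t test against 81.3% adjusted when surgeon explained nothing. It was 79.5% against 83.5% at a 10% share with the 2 mmHg effect. The cost seen with fixed terms at zero variance did not appear.

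**4. Validity of the t test.** Under no device difference, the mean estimate was within 0.02 mmHg of zero and type I error was 4.3% to 5.0% in every unstratified setting. If the code is in fact stratified by surgeon and prior surgery, the same t test became conservative (3.5% to 4.2%), while the model containing the strata held 4.8% to 5.0%.

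**5. Size of chance imbalance.**
- Prior surgery: with half of eyes previously operated, the between-group gap has SD √(0.25 × 2/152) = 5.7 percentage points. A gap above 10 points has probability about 8%. With a 2 mmHg effect, a 10-point gap moves the estimate by 0.2 mmHg.
- Surgeon: imbalance contributes √(2 × share × 34.81/137) = 0.16, 0.23 or 0.32 mmHg (SD) for shares of 5%, 10% and 20%. This is already inside the total SE of 0.71.
- Per surgeon: assuming equal volumes (304/14, about 22 each) and simple randomization, a 15:7 split or worse has probability 2 × P(Bin(22, 0.5) ≤ 7) = 13.4%, or 14 × 0.134 = 1.9 surgeons on average.

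**The case against.** The strongest reply is that nothing here is an error. An unadjusted t test in an individually randomized trial is valid, its standard error already allows for chance imbalance, the planned size reproduces, and the variation in technique is deliberate, with generalizability as the stated reason. All of that stands. Adjustment is a choice about efficiency.

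A reader might infer more from the 13.4% figure: that device and surgeon effects are confounded. The documents do not support this. Sections 5.5 and 5.6 randomize subjects, not surgeons, so uneven splits arise only by chance and largely offset in the pooled estimate, as steps 4 and 5 show. Nor do the documents show that the code is unstratified; Section 5.6 is silent. Equal volumes of about 22 per surgeon and simple randomization are assumptions.

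It is also fair to say that the gains in step 2 are best-case, and that nothing in the documents makes surgeon and prior surgery the main sources of variation. Baseline IOP is recorded too.

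What remains is that the plan admits these sources of variation, has no spare power, and can adjust at almost no cost. Its silence on strata also leaves it unclear whether the named test matches the allocation.

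**Conclusion.** The point holds as a minor one about efficiency and prespecification. The named analysis is unbiased with correct type I error under unstratified allocation, and 152 per group is not too small, because 5.9 mmHg serves as a total SD for an unadjusted comparison.

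The loss is modest: at best 0 to 8 points of power if the two factors explain 0% to 20% of variance, and about 0 to 4 points in simulation with a surgeon share up to 10% and a prior-surgery effect up to 2 mmHg. These ranges rest on assumed variance shares, half of eyes previously operated and about 14 surgeons. They also take year 1 IOP, on which the sample size is based, as the outcome. The inference that device and surgeon effects are confounded should not be drawn.

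**What to change.** **Section 8.1.4.** Replace the unadjusted t test for year 1 IOP with a prespecified linear mixed model: treatment and prior intraocular surgery (yes/no) as fixed effects and a random intercept for operating surgeon. Report the adjusted difference in mmHg with its 95% confidence interval. Include any factor by which the randomization code is stratified. The unadjusted t test can be kept as a sensitivity analysis.

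**Section 5.6.** State how the code is generated: simple, blocked or stratified, and by what. Stratifying by prior surgery is optional. Stratifying by surgeon is not required: 14 surgeons by two strata gives 28 cells of about 304/28 = 11 patients, and small blocks handled by unmasked surgeons make allocation easier to guess.

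**Section 5.5.** Add operating surgeon to the recorded data; prior procedures are already there.

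**Cost.** Protocol wording, one extra data item and slightly more analysis work. With a random intercept the expected power loss is negligible if the factors explain nothing; with fixed surgeon terms it would be about 1 to 2 points.
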